14.5. Interim Analyses and Stopping Rules

There will be no formal interim analyses of outcomes; accumulating data will be reviewed at least annually by the Independent Data Monitoring Committee (IDMC). There will be no stopping rule as it is unlikely that there will be sufficient data for formal comparison.

14.6. Internal pilot

The internal pilot will assess trial progress at end of month 15 (9 months after accrual opens). Trial progress will be assessed by:

- Overall recruitment (total patients/month from expected 11 centres): red <2; amber 2-3; green >3
- Acceptance of randomised allocation: red <80%, amber 80-90%, green >90%

The internal pilot will be considered successful and the trial will continue as planned if both sets of criteria are "green". Where both recruitment and acceptance of allocated treatment are red, discussions will be held with the funder and trial oversight committees to establish where amendments could be put in place to address these issues. Where recruitment or acceptance is amber or red, screening logs will be reviewed and centres surveyed to understand and address reasons behind this, and findings discussed with funder and trial oversight committees. If either remains red by month 21, the trial will be considered unfeasible. Where either remains amber, recruitment and/or acceptance will be reviewed 3-monthly until green.

15. TRIAL MANAGEMENT

15.1. Trial Management Group (TMG)

A Trial Management Group (TMG) will be set up and will include the Chief Investigator, ICR-CTSU Scientific Lead, Co-investigators and identified collaborators, the Trial Statistician and Clinical Trials Programme Manager and Trial Manager. Principal Investigators and key study personnel will be invited to join the TMG as appropriate to ensure representation from a range of sites and professional groups. Where possible, membership will include a lay/consumer representative. The TMG will meet at regular intervals, and at least annually. Notwithstanding the legal obligations of the Sponsor and Chief Investigator, the TMG have operational responsibility for the conduct of the trial. The Committee's terms of reference, roles and responsibilities will be defined in a charter issued by ICR-CTSU.

15.2. Trial Steering Committee (TSC)

The ICR-CTSU Breast RT Trials Steering Committee will provide strategic oversight of the study on behalf of the funder and sponsor. The TSC will meet at regular intervals, and at least annually. The Committee's terms of reference, roles and responsibilities will be defined in charter issued by ICR-CTSU.

15.3. Independent Data Monitoring Committee (IDMC)

An Independent Data Monitoring Committee (IDMC) will be set up to monitor the progress of the trial and will comprise a Chair and at least two further members with clinical or statistical expertise (at least one member must be a statistician). Membership of the IDMC will be proposed by the TMG and approved by the TSC.

The IDMC will meet in confidence at regular intervals, and at least annually. A summary of findings and any recommendations will be produced following each meeting. This summary will be submitted to the TMG and TSC, and if required, the main REC.

The IDMC will reserve the right to release any data on outcomes or side-effects through the TSC to the TMG (and if appropriate to participants) if it determines at any stage that the combined evidence from this and other studies justifies it.

The Committee's terms of reference, roles and responsibilities will be defined in a charter issued by ICR-CTSU.

16. RESEARCH GOVERNANCE

16.1. Sponsor Responsibilities

The Sponsor of this clinical trial is the Institute of Cancer Research (ICR).

16.2. Participating Site Responsibilities

Responsibilities delegated to participating sites are defined in an agreement between the Sponsor and the individual site. The Principal Investigator is responsible for the trial team and trial conduct at the participating site.

17. TRIAL ADMINISTRATION & LOGISTICS

17.1. Site Activation

Before activating the trial, participating sites are required to sign an agreement accepting responsibility for all trial activity that takes place within their site.

Sites may commence recruitment once the site agreement has been signed by all required signatories, the required trial documentation is in place (as specified by ICR-CTSU) and a site initiation (visit or teleconference) has taken place. Site initiation visits will be conducted at sites where the Principal Investigator has requested one or where ICR-CTSU deems it is appropriate.

17.2. Investigator Training

Each centre should complete the comprehensive pre-trial section of the radiotherapy quality assurance programme prior to commencing recruitment, as detailed in the PARABLE Radiotherapy Planning and Delivery guidelines ("Radiotherapy Quality Assurance (RTQA) Pack"). In addition to this, again prior to commencing recruitment, centres will need to complete QA training in contouring and planning according to the schedule described in the RTQA pack.

17.3. Data Acquisition

Electronic (e) Case Report Forms (CRF) will be used for the collection of trial data. ICR-CTSU will provide guidance to sites to aid the completion of the eCRFs. The Trial Management Group reserves the right to amend or add to the eCRF template as appropriate. Such changes do not constitute a protocol amendment, and revised or additional forms should be used by sites in accordance with the guidelines provided by ICR-CTSU.

Patient Reported Outcomes will be collected using paper questionnaires following current Standard Operating Procedures within ICR-CTSU. However, it may be possible to utilise electronic data collection systems in future when available. An embedded Study Within a Trial will explore options for collecting acute toxicity assessments from patients.

Radiotherapy treatment DICOM data will also be collected. Guidelines on DICOM data submission will be given in the PARABLE RTQA pack

17.4. Central Data Monitoring

Once data has been entered on the eCRF by the site personnel, ICR-CTSU will review it for compliance with the protocol, and for inconsistent or missing data. Should any missing data or data anomalies be

found, queries will be raised for resolution by the site. Any systematic inconsistencies identified through central data monitoring may trigger an on-site monitoring visit.

17.5. On-Site and Remote Monitoring

On-site monitoring visits or remote monitoring sessions may be conducted by ICR-CTSU in order to review essential documentation and carry out source data verification to confirm compliance with the protocol, in accordance with the study monitoring plan. If an on-site monitoring visit/remote monitoring session is required, ICR-CTSU will contact the site to make the necessary arrangements Once a date has been confirmed, the site should ensure that full patient notes of participants, including electronic notes, selected for source data verification are available for monitoring. If any problems are detected during the course of monitoring activities, ICR-CTSU will work with the Principal Investigator or delegated individual to resolve issues and determine appropriate action.

17.6. Completion of the Study and Definition of Study End Date

The study end date is deemed to be the date of last data capture.

17.7. Archiving

Essential trial documents should be retained according to local policy and for a sufficient period for possible inspection by the regulatory authorities (at least 5 years after the date of last data capture). Documents should be securely stored and access restricted to authorised personnel.

18. PATIENT PROTECTION AND ETHICAL CONSIDERATIONS

18.1. Risk Assessment and Approval

This trial has been formally assessed for risk and approved by the Sponsor's Committee for Clinical Research.

18.2. Public and Patient Involvement

Patient advocates were involved in all aspects of the trial including study design/methodology, sample collection, patient information and consent forms and are represented on the TMG.

18.3. Ethics Approvals

The trial will not commence at any participating site until the required approvals are in place. ICR-CTSU, on behalf of the Sponsor, will ensure that the trial has received ethics approval from a research ethics committee (REC) for multi-centre trials, HRA approval and relevant NHS Permissions. Before recruiting patients, the Principal Investigator at each site is responsible for obtaining local approvals.

18.4. Trial Conduct

This trial will be conducted according to the approved protocol and its amendments, supplementary guidance and manuals supplied by the Sponsor and in accordance with the UK Policy Framework for Health and Social Care and the principles of GCP.

18.5. Informed Consent

The Principal Investigator retains overall responsibility for the conduct of research at their site; this includes the taking of informed consent of participants. The PI must ensure that any person delegated responsibility to participate in the informed consent process is duly authorised, trained and competent to do so in accordance with the ethically approved protocol, principles of Good Clinical Practice and Declaration of Helsinki.

Patients should be asked to sign the current ethics approved PARABLE consent form at trial entry after receiving both verbal and written information about the trial, having been given sufficient time to consider this information. All consent forms must be countersigned by the Principal Investigator or a designated individual. A signature log of delegated responsibilities, listing the designated individuals and the circumstances under which they may countersign consent forms, must be maintained at the participating site. This log, together with original copies of all signed patient consent forms, should be retained in the Site Investigator File and must be available for inspection. The current ethics approved PARABLE patient information sheets should be provided in addition to any standard patient information sheets that are provided by the site and used in routine practice.

18.6. Patient Confidentiality

Patients will be asked to consent to their full name being collected at trial entry in addition to their date of birth, hospital number, postcode and NHS number or equivalent to allow linkage with routinely collected NHS data and ensure accuracy in handling biological samples.

Each investigator should keep a separate log of all participants' Trial IDs, names, addresses and hospital numbers. The investigator must retain trial documents (e.g. participants' written consent forms) in strict confidence. The investigator must ensure the participants' confidentiality is maintained at all times.

Representatives of ICR-CTSU will require access to participants' hospital records for quality assurance purposes. ICR-CTSU will maintain the confidentiality of participants at all times and will not reproduce or disclose any information by which participants could be identified.

18.7. Data Protection

All investigators and trials staff must comply with applicable data protection laws at all times.

18.8. Liability

Indemnity to meet the potential legal liability of investigators participating in this trial is provided by the usual NHS indemnity arrangements.

19. FINANCIAL MATTERS

This trial is investigator designed and led. ICR has received funding from National Institute for Health Research (NIHR) for the central coordination of the trial. The trial meets the criteria for R&D support as outlined in the Statement of Partnership on Non-Commercial R&D in the NHS in England. The trial is part of the National Institute for Health Research Clinical Research Network (NIHR CRN) portfolio by virtue of its funding by the NIHR and for similar networks in the three devolved UK nations. NIHR CRN (and their equivalents in the devolved UK nations) resources should therefore be made available for the trial to cover UK specific research costs

20. PUBLICATION POLICY

The main trial results will be published in a peer-reviewed journal, on behalf of all collaborators. The manuscript will be prepared by a writing group, consisting of members of the TMG. Participating clinicians may be selected to join the writing group on the basis of intellectual and time input. All participating clinicians will be acknowledged in the publication.

Any presentations and publications relating to the trial must be authorised by the TMG. Authorship of any secondary publications e.g. those relating to sub-studies, will reflect intellectual and time input into these studies. Authorship of all publication will usually be in accordance with ICMJE guidance.

No investigator may present or attempt to publish data relating to the PARABLE trial without prior permission from the TMG.

21. ASSOCIATED STUDIES

21.1. Translational Study

Subject to patients' written informed consent, baseline blood samples will collected for future translational sub-studies, which will be defined separately.

Subject to patients' written informed consent, archival tissue samples (FFPE blocks) of primary tumour collected at the time of diagnosis or any other applicable surgical procedures (including subsequent disease relapses or new primary cancers) will be requested. Associated information, including imaging scans carried out at the time of any relapse as part of standard care will also be requested.

Tissue samples are prospectively collected for use in future translational sub-studies which will be defined separately.

21.2. Study within a Trial (SWAT): PBT Trials Recruitment Study

PARABLE, along with other trials involving PBT, provides an opportunity to explore possible barriers to recruitment for PBT trials and to inform future trial design and development. An embedded 'Study within a Trial' (SWAT) will utilise a questionnaire to identify barriers to recruitment for PBT trials, assess the accessibility of PBT for the target population, and assess the generalisability of results from PBT trials to the target population.

23. APPENDICES

A1 AGE AND RISK ADJUSTED TABLE FOR ASSESSMENT OF ELIGIBILITY

The table below shows Mean Heart Dose (MHD) Thresholds on the standard radiotherapy plan that confer around 2% or higher absolute risk of **radiation-related disease**: major cardiac event - MCE (including fatal) or unstable angina by age 80 years, adapted from Darby *et al* Appendix Table S13(10). Table S13 modelled the risks of receiving breast radiotherapy at age 40, 50, 60 and 70 years. The age groupings by decade in this table reflect these ages at the mid-point and include women <40 and >70 years.

Update to MHD thresholds in protocol v4.0

The PARABLE trial has been recruiting steadily using mean heart dose eligibility thresholds determined using data from Darby et al (2013). These were rounded up to the nearest 0.5Gray at the outset of the trial for simplicity. However, it has been noted that several patients just miss eligibility thresholds, as a result of the rounding, meaning that patients who could potentially benefit from PBT are unable to participate. In addition, the contribution of the breast tumour bed boost dose to the mean heart dose is not currently considered as it was felt, prior to the trial opening, that this was likely to be negligible. However, it has become apparent that some patients narrowly miss out on randomisation due to the combination of rounding down and omitting the small, but not insignificant, contribution of the breast tumour bed boost dose to the mean heart dose. A revised table has therefore been prepared with estimated mean heart dose thresholds to the nearest 0.1Gy and which takes account of the contribution of the breast tumour bed boost to mean heart dose. These changes should enable more women in the appropriate cardiac risk category to be included in the trial. There will be no impact on the statistical design of the trial.

| Age (years) at study registration | Mean heart dose (Gy) needed for around 2% or higher risk of radiation-related heart disease by aged 80 years | | | |
|---|--|---------------------|-----------------------------------|---------------------|
| | No Cardiac Risk Factor | | At Least One Cardiac Risk Factor* | |
| | No boost ^{\$} | Boost ^{\$} | No boost ^{\$} | Boost ^{\$} |
| ≤44 [¶] | ≥4 Gy | ≥3.7 Gy | ≥2.4 Gy | ≥2.1 Gy |
| 45-54 | ≥6 Gy [#] | ≥6 Gy [#] | ≥3.6 Gy | ≥3.3 Gy |
| 55-64 | ≥6 Gy [#] | ≥6 Gy [#] | ≥4.3 Gy | ≥4.0 Gy |
| 65+ | ≥6 Gy [#] | ≥6 Gy [#] | ≥5.3 Gy | ≥5.0 Gy |

[¶] Incorporating data for women <40 years (Henson et al)⁽¹⁹⁾.

*Cardiac Risk Factors include:

Pre-existing cardiac disease:

Myocardial infarction or coronary revascularisation procedure

[#]Represents clinically acceptable threshold for mean heart dose based on RCR UK consensus⁽⁹⁾.

^{\$} Represents boost to breast tumour bed only (ie does not refer to nodal boosts)

Pericarditis, endocarditis, myocarditis Cardiac valve disorders Cardiomyopathy Cardiac arrhythmia or conduction disorders Heart Failure, including

- Confirmed diagnosis of heart failure in medical notes. This usually covers symptomatic
 patients with heart failure at any level of LVEF: heart failure with reduced ejection
 fraction (<40%), heart failure with mild reduced EF (40-49%) and heart failure with
 preserved ejection fraction (>50%). This is whether caused by cancer treatment or preexisting prior to cancer therapy.
- Moderate or severe asymptomatic cancer therapy-related cardiac dysfunction. This
 includes patients who have asymptomatic LV dysfunction detected on surveillance and
 where their LVEF has fallen to <50% (40-49% = moderate, <40% = severe). They can be
 included if any history of CTRCD, even if recovered with cardiac treatment. These cases
 could all be classified as 'asymptomatic heart failure' and in the US would be Stage B
 heart failure(49).

Other Circulatory Diseases:

Hypertension

Cerebrovascular disease

Peripheral vascular disease

Pulmonary Embolism or Deep Vein Thrombosis (Long-line DVTs count as a cardiac risk factor, but pregnancy-related DVTs do not)

Other:

Diabetes

Chronic obstructive pulmonary disease

Body Mass Index >30 kg/m²

Smoking: defined as long term continuous smoking in the year prior to study registration.

This list summarises the codes from International Classification of Diseases (10th revision, I-00 to I-15 and I-20 to I-99) and risk factors used in model by Darby et al.

A2. MECHANISTIC SUB-STUDY

A2.1 PARABLE RBE Modelling

While PBT offers more conformal physical doses than conventional RT, the complex difference in the biological effect of a given dose of PBT vs RT (known as the Relative Biological Effectiveness, RBE) is less well known. Current clinical PBT practice assumes a fixed RBE of 1.1 for PBT. However, it is known that RBE depends on both the dose delivered and the Linear Energy Transfer (LET) of the protons that deliver the dose. Proton LET increases with decreasing particle energy: lower energy protons towards the end of their range have higher LETs and thus RBEs.

These effects are potentially significant because many protons reach end-of-range in normal tissues, and elevated RBEs in these tissues may impact significantly on side-effects. Variable RBE algorithms considering this could help fine-tune PBT planning, but these have seen limited clinical testing (30).

Recent prospective single cohort studies (31, 32) suggest that end of range increases in RBE may not be significant for breast patients. However, post-radiotherapy CT scans in breast patients can be used to quantify asymptomatic lung changes, providing a highly informative experimental model for measuring end-of-range RBE and testing variable RBE algorithms (33).

The PARABLE cohort offers a unique opportunity to address this mechanistic challenge, to test internationally developed RBE models for PBT by comparing calculated doses with serial changes in lung density. This will be achieved through a series of steps:

1. Apply validated Monte Carlo radiotherapy models to determine patient LET distributions

LET is not calculated as part of current PBT planning. To provide necessary information for subsequent analyses, we have already set up a framework for Monte Carlo simulations to be performed for optimised treatment plans (50). Our simulations enable us to generate both dose and associated LET maps, as shown in the figure below. These maps will be used to evaluate the range of LET values present in the lung from end-of-range protons, a key driver of subsequent RBE effects.

[figure not shown]

Figure: Dose and LET maps calculated for a PARABLE treatment plan using our Monte Carlo simulation framework (based on GATE/GEANT4). Maps thresholded at 2% of the prescription dose. The contours in white show the $PTV_{low} + PTV_{high}$ regions. The right figure shows that 50% of the total left lung volume receives an LET greater than 7 keV/ μ m.

2. Validate elevated RBE of end-of-range protons for radiographic lung changes

It was recently demonstrated in a small, retrospective study (33) that end-of-range protons led to greater radiographic changes in the lung than photons at similar dose levels. As a first step, we will replicate this analysis in this larger, prospective dataset. We will quantify radiographic changes in the lung as a function of dose in proton and photon therapy patients, and test if there is a statistically significant difference between these two treatment modalities above and beyond the clinically-accepted value of 1.1. This will represent the first validation of a variable proton RBE in a prospective clinical trial, and provide an essential starting point for future analysis.

3. Establish uncertainty bounds for proton RBE as a function of dose and LET

With evidence of an elevated proton RBE, we will then seek to parameterise the possible values of proton RBE in a model-independent fashion. As a first step, we will parameterise radiographic changes as a function of dose in the low-LET photon cohort. This will then be used to calculate RBEs for lung changes in our proton treatment plans, as a function of both dose and LET. By mapping out the variation of RBE with these parameters, we will be able to establish confidence bounds that must be satisfied by any model applied to these systems, potentially significantly restricting the parameter space for some models and possible forms for the dose-LET-RBE relationship.

4. Test predictive power of published models to predict serial lung changes

Finally, using these datasets showing the relationship between dose, LET and lung changes, we will seek to test a range of published RBE models to determine if they effectively predict the relationship between these parameters, and provide estimates of the uncertainty range on parameters of these models.

A range of proton RBE models have been published. These include purely phenomenological models which parameters linear quadratic model parameters as a function of LET (43, 51, 52), recently reviewed by Rorvik et al(53). There are also a range of other mechanistic models including the Local Effect Model, the Microdosimetric Kinetic Model, the Monte Carlo Damage Simulation, MEDRAS, and the Manchester Model. Significantly, while these models often differ in assumptions or fitting data, many show very similar dependencies between dose and LET which would be tested in this model.

To evaluate the applicability of these models for radiographic lung changes, we will generate RBE-weighted dose maps for a set of models. Although they are built on different assumptions and datasets, almost all phenomenological models show a linear dependence of RBE on LET at typical proton LETs, and so as an exemplar of this class of model, we will apply the McNamara model. Other mechanistic models include a range of different dependencies on LET. To evaluate a reflective sample of these, we will also generate RBE-weighted dose maps for the MKM, MEDRAS, and the Manchester model.

For all of these models, we will evaluate the correlation between the model predicted and observed RBEs, determining which offer superior predictive power. This information will be used to stratify models in terms of their accuracy, and identify areas where further data may help refine these models and translate them towards clinical practice.

A3. PATIENT-REPORTED OUTCOMES

Rationale for PRO measurement

PARABLE aims to test whether PBT reduces risk of serious RT-induced heart toxicity many years after RT without increasing shorter-term adverse effects compared with tailored photon RT. To this end, co-primary endpoints have been selected to address each of these aspects. Patient-reported breast symptoms at 2 years is a co-primary endpoint in PARABLE, selected to test whether PBT is non-inferior to tailored RT in terms of breast adverse effects in the shorter-term.

PRO evaluations in PARABLE are based on standardised measures that will provide data and allow comparison with other relevant trials. The scales selected include specific measures for evaluating breast cancer therapies, body image, protocol-specific post RT symptoms, a general cancer health related quality of life scale and a generic quality of life scale widely used in health economic evaluations. These measures have been used in the START, IMPORT and FAST-Forward breast radiotherapy trials. Assessment will be carried out over at least 5 years of follow-up. Timings of assessments are in line with those used in the START, IMPORT and FAST-Forward radiotherapy trials.

The PRO early toxicity assessments in PARABLE build on the FAST-Forward acute toxicity sub-study and include additional endpoints proposed during patient focus group discussions informing design of the PARABLE trial. An embedded 'Study Within A Trial' will refine the acute toxicity PRO study.

Measures

EORTC QLQ-C30 is a 30-item cancer quality of life-specific instrument, which comprises 5 functional sub-scales, 2 symptom subscales and additional symptom items and questions about global health and global quality of life (54).

EORTC QLQ-BR23 breast cancer module is a 23-item scale designed for use in breast cancer treatment [4]. It consists of 6 subscales: breast symptoms, arm symptoms, body image, systemic side effects, sexual functioning, sexual enjoyment and items on hair loss and future perspective (55).

10-item Body Image Scale (BIS) (of which 4 items are already incorporated in the BR23) was designed for use with cancer patients and has been widely used in national breast cancer treatment trials (56).

Protocol-specific items as used in previous breast RT trials: 6 items specific to post-treatment effects evaluating change in skin appearance, change in overall appearance of the breast, breast shrinkage and hardening, position of the nipple and difficulty getting a bra to fit. An additional item measures shoulder stiffness. Also items relating to acute breast and skin changes during and immediately after radiotherapy, as used in the FAST-Forward acute toxicity study.

PRO-CTCAE items relating to acute toxicities including skin darkening, mouth or throat sores, cough (57).

EQ-5D-5L is a generic measure of health-related quality of life comprising 5 domains (mobility, self-care, usual activities, pain/discomfort, anxiety/depression) and a visual analogue scale that assesses health state (58).

Timing of data collection

Participants will be asked to complete questionnaire booklets in clinic weekly for the 3 weeks of radiotherapy treatment; subsequent acute toxicity questionnaires will be sent to participants' homes by ICR-CTSU, with subsequent questionnaires being sent to participants' homes by ICR-CTSU at 6, 12, 24 and 60 months from commencing treatment.

A4. GLOSSARY

| CT | Computerised tomography | | |
|----------|---|--|--|
| CTCAE | Common Terminology Criteria for Adverse Events | | |
| CTRad | Clinical and Translational Radiotherapy Research Working Group | | |
| CTU | Clinical trials unit | | |
| DIBH | Deep inspiration breath hold | | |
| EORTC | European Organisation for Research and Treatment of Cancer | | |
| ePRO | Electronic patient-reported outcomes | | |
| EQ-5D-5L | EuroQol 5-dimension 5-level | | |
| Gy | Gray, unit of radiation dose | | |
| HRA | Health Research Authority | | |
| HU | Hounsfield Units | | |
| ICR-CTSU | The Institute of Cancer Research Clinical Trial and Statistics Unit | | |
| IDMC | Independent data monitoring committee | | |
| IMN | Internal mammary nodes | | |
| IMRT | Intensity modulated radiotherapy | | |
| ISRCTN | International Standard Randomised Controlled Trial Number | | |
| NCRI | National Cancer Research Institute | | |
| NHS | National Health Service | | |
| NHSE | National Health Service England | | |
| NICE | National Institute for Health and Care Excellence | | |
| NIHR | National Institute for Health Research | | |
| PBT | Proton beam therapy | | |
| PPI | Patient and Public Involvement | | |
| PRO | Patient-reported outcomes | | |
| QLQ-BR23 | Quality of Life of Cancer Patients – breast cancer module | | |
| QLQ-C30 | Quality of Life of Cancer Patients – core questionnaire | | |
| RBE | Relative biological effectiveness | | |
| RCR | Royal College of Radiologists | | |
| RCT | Randomised controlled trial | | |
| RT | Radiotherapy | | |
| RTOG | Radiation Therapy Oncology Group | | |
| RTTQA | Radiotherapy Trials Quality Assurance | | |
| SWAT | Study within a trial | | |
| TMG | Trial management group | | |
| TSC | Trial steering committee | | |
| UCLH | University College London Hospital | | |

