14.3.3.2 Correlation of RBE-weighted dose maps with radiological changes in lungs and ribs

In patients randomised to PBT, doses to lungs and ribs on RBE-weighted dose maps for the 3 selected variable and standard RBE 1.1 models will be compared with radiological changes in lungs (lung fibrosis) and ribs (rib fractures and/or increased rib density). Candidate RBE models have been selected representing a phenomenological approach (McNamara model(43)), LET-weighted dose (McMahon(42)) and a mechanistic approach (Microdosimetric-Kinetic (44)).

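### Appendix A2.1 makes the RBE bounds by dose and LET follow only a positive PBT-photon test, so a null test would leave the mechanistic study without them

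*Protocol*

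**What the plan says.** Appendix A2.1 describes the RBE work as a sequence of steps.

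- **Step 2** carries no condition. It promises "We will quantify radiographic changes in the lung as a function of dose in proton and photon therapy patients", and then to "test if there is a statistically significant difference between these two treatment modalities above and beyond the clinically-accepted value of 1.1".
- **Step 3** opens "With evidence of an elevated proton RBE, we will then seek to parameterise the possible values of proton RBE in a model-independent fashion". It takes the photon dose-response as reference, calculates RBE in the proton plans by dose and LET, and says of the result that "we will be able to establish confidence bounds that must be satisfied by any model applied to these systems".
- **Step 4** tests published models. It does not repeat the condition, but it states that "we will evaluate the correlation between the model predicted and observed RBEs, determining which offer superior predictive power", and observed RBEs are what step 3 calculates.

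Before the steps, the appendix cites prospective single-cohort studies which "suggest that end of range increases in RBE may not be significant for breast patients".

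The main text attaches no condition to its own versions of this work. Section 14.3.3.2 says "RBE-weighted dose maps for the 3 selected variable and standard RBE 1.1 models will be compared with radiological changes in lungs" (and ribs). Section 14.4 compares lung HU/Gy between arms and relates each RBE model to lung fibrosis and rib fracture, again unconditionally.

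**The concern.** As worded, estimation depends on a test result in the same data. An interval estimate is worth having whichever way the test falls, and worth most when the test is null, because the useful finding is then how large an RBE the data exclude. A2.1 says what happens when step 2 is positive and nothing about the other case.

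On the protocol's own account a null is a live possibility. The appendix cites prospective cohorts pointing that way, and the positive evidence used for planning in section 14.1 is one retrospective comparison with 10 patients per group. The bounds are meant to constrain any RBE model and to inform planning beyond this trial, so they should not exist only when a test succeeds.

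This is a stated order and condition, not a detail left open. A statistical analysis plan that followed A2.1 would inherit it.

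**Working it through.** **Inputs from section 14.1 (lung HU/Gy comparison).** 96 per group, 10% unevaluable, SD 1.1 HU/Gy, design difference 0.55 HU/Gy (0.5 SD), two-sided alpha 0.05, stated power 90%. The earlier retrospective estimate is 1.08 HU/Gy in absolute size (0.98 SD).

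**Assumptions.** The clause in step 3 acts as a gate, and the gate is significance at two-sided 0.05 in the expected direction. A2.1 states no alpha, so 0.05 is borrowed from section 14.1. True effects below 0.5 SD are illustrative; the protocol gives none.

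**Step 1: reproduce the stated power.** Evaluable per arm = 96 × 0.9 = 86.4, taken as 86. SE of the standardised difference = √(2/86) = 0.1525. Then 0.5/0.1525 = 3.28, and power = Φ(3.28 − 1.96) = 0.906 (0.903 from the noncentral t). The 90% reproduces.

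**Step 2: what survives a null.** SE in HU/Gy = 1.1 × 0.1525 = 0.168. The 95% half-width = 1.96 × 0.168 = 0.33 HU/Gy, whatever the test result. A non-significant difference is smaller than 0.33 in absolute size, so its interval reaches at most 0.33 + 0.33 = 0.66 HU/Gy, short of the earlier 1.08. The data would therefore be informative under a null. But this is a bound on a mean HU/Gy difference, not on RBE by dose and LET.

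**Step 3: how often step 3 would be skipped, and selection on the HU/Gy scale.** With θ = (true effect in SD)/0.1525, P(significant) = Φ(θ − 1.96). The mean standardised estimate given significance is θ + φ(1.96 − θ)/Φ(θ − 1.96), and the inflation factor is that mean divided by θ. At 0.5 SD: 3.28 + 0.167/0.906 = 3.46, and 3.46/3.28 = 1.06.

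| True effect (SD) | Power | Step 3 skipped | Inflation if significant |
|---|---|---|---|
| 0.98 (earlier estimate) | about 100% | about 0% | 1.00 |
| 0.5 (design) | 91% | 9% (10% with the t) | 1.06 |
| 0.4 (assumed) | 75% | 25% | 1.16 |
| 0.3 (assumed) | 50% | 50% | 1.40 |
| 0.2 (assumed) | 26% | 74% | 1.95 |

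Simulation with 2,000,000 draws agreed with the factors at 0.98, 0.5, 0.3 and 0.2 SD.

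**Step 4: what depends on step 3.** Inputs to step 4 come from step 1 (LET) and step 2 (lung change by dose), both unconditional. Observed RBEs come only from step 3. With step 3 skipped, the model analyses of sections 14.3.3.2 and 14.4 could still run, but the predicted-against-observed RBE correlation in A2.1 could not.

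**The case against.** The strongest reply is that no gate was intended. The opening clause has no threshold, alpha or stop instruction; the heading of step 3 is unconditional; and step 2 is written in the same anticipatory tone. This is a fair reading, and it cannot be excluded. But the clause follows directly on a significance test, no alternative branch is given, and an analyst could follow it literally. If only an expectation was meant, the change simply records that intent.

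A second reply is that a null would not leave the trial silent. That stands: the HU/Gy difference and its interval are unconditional, and step 4 separately promises uncertainty ranges for the parameters of the published models. What would be lost is narrower: the model-independent RBE estimate by dose and LET, its bounds, and the observed RBEs.

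A reader might infer two stronger points, and the protocol supports neither.

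- **That any RBE the trial reports is inflated by selection.** The inflation is about 6% at the design effect and nil at the earlier estimate. The larger factors need assumed effects below about 0.4 SD. They apply to a mean HU/Gy difference, and the protocol gives no conversion to RBE.
- **That A2.1 contradicts section 14.3.3.2.** The model comparison there corresponds to step 4, which carries no condition of its own. The passages can be read together; only the reliance on observed RBEs ties step 4 to step 3.

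It is also fair that this is mechanistic work and leaves the co-primary endpoints and the sample size untouched.

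**Conclusion.** The point holds in a limited form. Taken literally, A2.1 produces its RBE bounds by dose and LET only after a positive test in the same patients, and so withholds them when they would be most informative. Under the gate reading at two-sided 0.05, that happens in about 10% of trials at the design effect and about 50% at an assumed 0.3 SD, with 86 evaluable per arm and SD 1.1. Selection bias is a secondary matter: removing the condition leaves the estimate from a significant trial unchanged and ensures that the other trials report one too. This is a free improvement to the wording, not a flaw in the main trial.

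**What to change.** Replace the opening sentence of step 3 in A2.1 with: *Whatever the result of step 2, we will estimate proton RBE as a function of dose and LET with confidence bounds.* Add to step 4 that it is likewise run and reported regardless of the step 2 result, consistent with sections 14.3.3.2 and 14.4.

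The cost is two sentences in an appendix. No further data, scans or patients are needed, since the analysis is already planned and uses CT and treatment-plan data that the trial collects anyway.
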